## **II. Protocol Objectives and Analysis Endpoints**

Objective	Endpoint (Assessment)
Phase 1	
Primary:	

Establish the safety, toxicity, and maximum tolerated dose (MTD) of the tinostamustine conditioning regimen.

Identify the recommended Phase 2 dose (RP2D) of tinostamustine for use in the

	

The number and frequency of DLTs, adverse events (AEs), serious adverse events (SAEs), neutrophil and platelet engraftment failure, treatment-related mortality (TRM) and transplant-related

Mundipharma-EDO GmbH / Protocol: EDO-S101-1004  
IQVIA Biotech (Confidential) Project # **CCI**

Objective	Endpoint (Assessment)
Phase 2 portion of the study.	non-hematologic Grade 3 toxicity over time through Day 30; as well as change from baseline in standard laboratory test, results and duration of cytopenia.
Secondary:	

Investigate the pharmacokinetics (PK) of tinostamustine.

	

Assessment of PK parameters.

Phase 2	
Primary:	

Investigate the efficacy of the tinostamustine conditioning regimen at the RP2D dose.

Investigate the safety of the tinostamustine conditioning regimen.

	

Objective response rate (ORR), and in patients treated at the RP2D (in Phases 1 and 2) who achieve CR, minimal residual disease-negativity (MRD-N) at Day 100 (<math>\pm 7</math> days) post-ASCT.

The number and frequency of adverse events (AEs), serious adverse events (SAEs), neutrophil and platelet engraftment failure, treatment-related mortality (TRM) and transplant-related non-hematologic Grade 3 toxicity over time through Day 30; as well as change from baseline in standard laboratory test results and duration of cytopenia.

Secondary:	

Evaluate the PK of tinostamustine.

	

Assessment of PK parameters.

### III. Study Design

#### A. Design Overview

This is a 2-part, international, multi-center, open-label study of salvage treatment with tinostamustine conditioning followed by ASCT in patients with relapsed/refractory MM.

**Phase 1** of the study employs a standard 3+3 dose escalation design with the objective of defining the DLTs of the tinostamustine conditioning regimen and defining the MTD and RP2D for use in the Phase 2 portion of the study. The initial dose of tinostamustine in the Phase 1 portion of the study is 180 mg/m^2, with escalation to 220, 260, and then 300 mg/m^2 or higher planned. If the 180 mg/m^2 dose level is not tolerable, then a lower tinostamustine dose of 160 mg/m^2 will be explored. Furthermore, if the 300 mg/m^2 is tolerable, with <33% of patients experiencing a DLT at this dose level, a dose higher than 300 mg/m^2 may be explored. The Safety Review Committee can make a decision to stop dose escalation or explore intermediary doses at any time.

Mundipharma-EDO GmbH / Protocol: EDO-S101-1004  
IQVIA Biotech (Confidential) Project # **CCI**

**Phase 2** of the study employs a 2-step sequential design. In Stage 1 of Phase 2, up to 31 patients initially will be enrolled. Recruitment will continue during the evaluation period needed for Stage 1 of Phase 2. If  $\leq 25$  patients of these initial 31 patients experience a response, then no additional patients will be enrolled. However, if  $> 25$  patients in Stage 1 of Phase 2 experience a response, then enrollment in this cohort will continue (Stage 2), with up to 71 patients enrolled. In Phase 2 of the study, all patients will receive tinostamustine at the RP2D administered in Phase 1 according to the same schedule.

## **B. Study Population**

Individuals eligible to participate in this study must meet the criteria listed in [Sections 5.1](#) and [5.2](#) of the protocol.

## **C. Sample Size Predictions**

Across both Phases 1 and 2 of the study, a total of up to ~86 patients may be enrolled.

A formal sample size determination/power calculation was not performed for the first phase of the study. Based on experience from previously published similar studies, a total number of 9 (minimum) to 12 (maximum) patients in the dose escalation stage of the study are foreseen.

For Phase 2 of the study, superiority testing will be performed to investigate the null hypothesis that the primary endpoint of responder rate is below or equal to the gold standard against the alternative hypothesis that it is higher than the gold standard. The gold standard is assumed to be 77.5% and a one-sided chi-square test will be performed at the 2.5% level of significance. For power considerations, the alternative working hypothesis is that the responder rate for the study treatment is at least 90%.

Using the methodology proposed by Simon and per the minimax design, 31 patients are to be enrolled in Stage 1. If  $> 25$  of 31 patients (in the Full Analysis Set [FAS]) in Stage 1 experience a response to treatment, then enrollment will continue into Stage 2, with up to 40 patients planned to be enrolled. However, if  $\leq 25$  patients in Stage 1 experience a response to treatment, no further patients will be enrolled (in the ongoing Stage 2 recruitment). Thus, a total of up to 71 patients will be enrolled in Phase 2.

If the total number of patients who experience a response is  $\geq 62$  of 71, then the study is considered a success.

## **D. Treatment Randomization**

Mundipharma-EDO GmbH / Protocol: EDO-S101-1004  
IQVIA Biotech (Confidential) Project # **CCI**

This is a non-randomized study. A patient will be considered enrolled when the patient has been consented and screened and when all eligibility criteria have been confirmed in the eCRF (electronic case report form).

#### **E. Assessment Schedule**

Please refer to [Table 1](#) of the protocol for the schedule of assessments.

Visits that subjects make to the clinic outside the assessment schedule are recorded as unscheduled visits.

### **IV. Interventions**

#### **A. Conditioning**

**CCI**

**CCI**

The drug substance is a class 4 cytotoxic agent and should be handled with care by experienced health care professionals. For administration, tinostamustine powder will be reconstituted with 20 mL saline (0.95) and the solution will be further diluted with saline to a final volume of 50 mL. Tinostamustine is to be administered IV through a Peripheral vein over 1 hour on Day -1.

**CCI**

#### **B. ASCT Infusion**

Patients will receive ASCs on Day 1. The ASCs will be infused via a central venous catheter using standard blood infusion tubing, per standard institutional practice.

### **V. General Analytical Considerations**

#### **A. Data Sources**

All data in the clinical database of this study will be collected via electronic case report forms (eCRFs) through remote data entry into InForm.

ECG data will be received via electronic data transfers from ERT.

In addition, PK serum data will be received via electronic data transfers from CSM for the analysis of PK parameters.

Mundipharma-EDO GmbH / Protocol: EDO-S101-1004  
IQVIA Biotech (Confidential) Project # **CCI**

[Sections 10.2.1](#) and [12](#) of the protocol provide additional details regarding study management.

#### **B. Definition of Baseline**

Tinostamustine is given 24 hours pre-ASCT on Day -1 (conditioning). Screening or last available observation prior to the tinostamustine dose will be considered as baseline. Where assessments are made the day of treatment that are scheduled per protocol to take place prior to treatment, it will be assumed that these pre-dose assessments will be baseline assessments.

The ‘study day’ variable in SDTM and ADaM is intended to capture the number of days since first exposure to the study treatment. Therefore, to comply with FDA guidelines, there will be no ‘study day’ value of 0. The conditioning dose of tinostamustine will start with ‘study day’ 1, and the ASCT will start with ‘study day’ 2. This ‘study day’ variable is separate from the time and events schedule specified in the protocol, where conditioning and ASCT would have taken place on Day -1 and Day 0, respectively. Therefore, any events after the tinostamustine dose, will be calculated as event date plus (+) number of days since the date of tinostamustine dose (‘study day’ 1). For any events prior to the tinostamustine dose date, the study date will be calculated as event date minus (-) the date of the tinostamustine dose date.

The data will be analyzed according to the visits recorded in the eCRF; no analysis windows will be applied.

#### **C. Missing Data**

Unless stated otherwise, missing data will not be replaced with imputed values. When relevant, sections below will address how missing data will be handled for the particular analyses.

#### **D. Covariate Adjustment in Primary Analysis**

No adjustments for covariates are planned for the analysis of primary or secondary endpoints.

#### **E. Sample Size Reassessment**

Not applicable.

#### **F. Interim Analyses or Timing of Analyses**

There will be no interim analyses for this study.

Mundipharma-EDO GmbH / Protocol: EDO-S101-1004  
IQVIA Biotech (Confidential) Project # **CCI**

## G. Test Sizes

Not applicable.

## H. Multiple Comparisons

Aside from the control of Type I error in the primary analysis of the primary endpoint, no control for the effect of multiple comparisons is planned.

## I. Analysis Populations

Four analysis populations will be defined for use with various analyses. The following table illustrates the relationship between each population and the analyses for which the data from the population will be used.

Analysis	Analysis Population			
	Safety	Full Analysis Set	Per-Protocol	Pharmacokinetic
Baseline	X			
Subject Disposition	X			
Efficacy		X	X	
Immunogenicity	X			
Safety	X			

### 1. Safety Population

The Safety Population includes all patients who receive tinostamustine.

### 2. Full Analysis Set

The Full Analysis Set (FAS) includes all patients in the Safety Population who had at least one post-ASCT response evaluation.

### 3. Per-Protocol Population

The Per-Protocol Population includes all patients in the Full Analysis Set with no major protocol deviations.

### 4. Pharmacokinetic (PK) Population

The PK Population includes all patients in the Safety Population with at least one quantifiable pre-dose and one quantifiable post-dose PK plasma concentration.

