
Day 1. If the CD34+ product is of large volume, the infusion can be given over 2 days.
 
Patients may receive the following supportive care:
 

IV hydration and anti-emetics, in accordance with institutional guidelines.

Growth factor support with pegfilgrastim or equivalent agent post-ASCT, in accordance with institutional guidelines.

Standard supportive care, in accordance with institutional guidelines, including blood product transfusions, antimicrobial prophylaxis, and treatment for febrile neutropenia.

		

Duration of Treatment and Study Duration:
 
All patients will receive 1 doses of tinostamustine on Days -1 followed by ASCT on Day 1.
 
The anticipated accrual is 9-12 patients/year in Phase 1. Recruitment will continue during the evaluation period needed for Stage 1 of Phase 2. All patients will be followed for a maximum of 130 (<math>\pm 7</math> days) post-ASCT thus yielding a study of total duration of approximately 2.5 to 3.5 years.
		

Criteria for Evaluation:
		

Efficacy Assessment(s):
 
Response will be determined by the Investigator using the IMWG criteria. In addition, response of each subject will be evaluated by two independent reviewers, otherwise not involved in the clinical trial. In order to assess response, M protein component is to be measured in serum and/or urine, free light chain (FLC) testing is to be performed. Note that in the case of immunoglobulin A (IgA) MM, MM IgA values should be used. Bone marrow aspirate or biopsy and imaging studies (e.g., computed tomography, magnetic resonance imaging) are to be performed as clinically indicated. For patients with CR, based on serum and urine analysis, bone marrow aspirate and biopsies are to be performed at Day 100 (<math>\pm 7</math> days), including the myeloma immunophenotype.
 
Confirmatory assessment: A second assessment of response will be conducted between 107 and 130 to confirm the response. If the result is not confirmed by a second evaluation, the status is either Non-Evaluable (NE) or the prior disease status remains valid. Confirmation should be obtained for biochemical markers but is not necessary for bone marrow or imaging studies.
 
Assessment of M protein in serum and urine should be performed any time relapse is suspected.
		

Name of Sponsor Mundipharma-EDO GmbH		

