
All patients in the safety set with at least one quantifiable pre-dose and one quantifiable post-dose PK plasma concentration will be included in the PK set.
 
Dependent of the specific analysis, these sets will be taken from the cohort for Phase 1, for Phase 2 (RP2D), or both phases pooled.
		

Efficacy Analyses:
 
Summaries for continuous and ordinal variables will include the number of observations (n), arithmetic mean, standard deviation (SD), median, minimum, and maximum. Summaries for categorical variables will include frequency counts and percentages.
 
Superiority testing will be performed on FAS in Phase 2 cohort to investigate the null hypothesis that the primary endpoint of responder rate is below or equal to the gold standard against the alternative hypothesis that it is higher than the gold standard. The gold standard is assumed to be 77.5% (CIBMTR report, December 2017) and a 1-sided, 2-step chi-square test will be performed at the 2.5% level of significance for FAS.
 
For the primary endpoint, also an upper 1-sided 97.5% confidence interval will be calculated for FAS in addition to summary statistics.
 
For the primary endpoint in other sets and for the secondary endpoints of other responder rates in the FAS, also 2-sided 95% confidence intervals will be calculated in addition to summary statistics.
		

Interim Analyses:
 
In Phase 2 of the study, at the completion of the Stage 1 with 31 patients, an interim analysis will be performed using the FAS for the Phase 2 cohort to determine whether enrollment will continue in Stage 2. If >25 of 31 patients in Stage 1 experience a response to treatment, then enrollment will continue into Stage 2, with up to 40 patients planned to be enrolled. However, if ≤25 patients in Stage 1 experience a response to treatment, no further patients will be enrolled (in the ongoing Stage 2 recruitment).
		

Pharmacokinetic Analyses:
 
PK analysis for tinostamustine and its metabolites will be performed using the PK set.
 
PK parameters at all doses will include maximum plasma concentration (<math>C_{max}</math>), time to maximum plasma concentration (<math>t_{max}</math>), half-life (<math>t_{1/2}</math>) area under the plasma concentration curve from 0 to 12 hours (<math>AUC_{0-12}</math>), area under the plasma concentration curve from time 0 to time t (<math>AUC_{0-t}</math>), apparent total clearance (CL/F),
		

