11. A triplicate ECG will be performed during Screening to determine patient eligibility for the study. Furthermore, on Day -1, a triplicate ECG is to be performed before study drug administration and a single ECGs will be performed at 30 and 60 minutes after the start of study drug administration for assessment by the site. Another single ECG will be performed at visit on day 30 ( $\pm 5$  days). ECGs are to be repeated by the Investigator, as clinically indicated.
12. Hematology parameters minimally include WBC count and differential (lymphocytes, monocytes, basophils, eosinophils, neutrophils), red blood cell (RBC) count, hematocrit, hemoglobin, and platelet count.
13. Serum chemistry parameters minimally include alanine aminotransferase (ALT), albumin, alkaline phosphatase (ALP), aspartate aminotransferase, (AST), bicarbonate, bilirubin (total, direct, and indirect), calcium, magnesium, chloride, glucose, lactate dehydrogenase (LDH), phosphate, potassium, sodium, and total protein.
14. Urinalysis includes appearance, color, pH, specific gravity, ketones, leukocytes, protein, glucose, bilirubin, urobilinogen, and occult blood.
15. The tinostamustine dose will be administered one day before ASCT (Day -1), at least 24 hours pre-ASCT.
16. Blood samples for PK are to be collected immediately pre-infusion of tinostamustine and 30, 45, and 60 ( $\pm 5$ ) minutes and then at 3, 6, and 24 hours ( $\pm 15$  minutes) and then 48 hours ( $\pm 30$  minutes) after the start of infusion. Blood samples for PK assessment should be collected following the 15-minute supine resting periods described for the continuous Holter recordings. PK samples are to be collected from the arm opposite of that used for tinostamustine administration.
17. On Day 1, ASCs will be administered IV according to standard institutional practice. If the CD34+ product is of large volume, the infusion can be given over 2 days.
18. A skeletal survey (plain radiographs, or any other method used as standard care at the site, of the skull, spine, ribs, pelvis, humeri and femora) will be performed at Screening if not performed within the previous 3 months. Thereafter, skeletal survey and/or other imaging studies are to be performed as clinically indicated.
19. Bone marrow aspirate and trephine biopsy are to be performed during Screening. Bone marrow aspirate and biopsy are to be repeated during treatment as clinically indicated, at the Investigator's discretion, and at any time CR is suspected.

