### **10.2.2. Analysis Populations**

All patients who receive tinostamustine will be included in the safety set.

All patients in the safety set who had at least one post-ASCT response evaluation will be included in the full analysis set (FAS).

All patients in the FAS with no major protocol deviations will be included in the per-protocol (PP) set.

All patients in the safety set with at least one quantifiable pre-dose and one quantifiable post-dose PK plasma concentration will be included in the PK set.

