#### **10.2.9. Pharmacokinetic Analyses**

PK analysis for tinostamustine and its metabolites will be performed using the PK set.

PK parameters at all doses will include  $C_{max}$ , time to maximum plasma concentration ( $t_{max}$ ),  $t_{1/2}$ , area under the plasma concentration curve from 0 to 12 hours ( $AUC_{0-12}$ ), area under the plasma concentration curve from time 0 to time t ( $AUC_{0-t}$ ), apparent total clearance (CL/F), apparent volume of distribution (Vd/F), and terminal disposition rate constant ( $\lambda_z$ ). The initial calculation of PK parameters will be performed using non-compartmental analysis. Plasma concentrations and PK parameters will be summarized by dose.

Summaries will include the number of observations (n), arithmetic or geometric mean, SD or coefficient of variation (CoV), median, minimum, and maximum.

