**Recommended Anti-Emetics**

Due to its association with QTc prolongation, ondansetron is prohibited around the time of tinostamustine dosing. Also, due to reported interactions with alkylating agents, aprepitant is also not allowed for nausea control. We, therefore, recommend the following anti-emetic medications for nausea control on day -1:

- Palonosetron
- Glucocorticoids-as single agent or in combination with palonosetron
- Olanzapine
- Lorazepam-in combination with other recommended anti-emetics

Given the short half-life of tinostamustine, ondansetron can be used up to 24 hours prior to tinostamustine dosing on day -1 and resumed 24 hours after the dose. In patients with mild hepatic dysfunction, this interval should be extended to 48 hours due to reports of delayed clearance of ondansetron in this population. Since aprepitant has a long half-life, it should not be administered at least 3 days prior to tinostamustine dosing. If needed, aprepitant can be given 24 hours after tinostamustine dosing.

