### **C. Study Conduct Changes**

Based on safety signals this study was halted, and later discontinued, to enhance the protection of subjects and to allow for further evaluation of the investigational product. As a result, the following analyses described in the protocol are no longer appropriate or applicable:

Phase 1 – number and frequency of DLTs, neutrophil and platelet engraftment failure, treatment-related mortality (TRM) and transplant-related non-hematologic Grade 3 toxicity over time through Day 30, results and duration of cytopenia, change from baseline in standard hematology and coagulation laboratory test

Phase 2 – neither the primary nor secondary objectives/endpoints will be explored.

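### The PK set requires a quantifiable concentration before the only tinostamustine dose, so as written it excludes essentially every correctly sampled Phase 1 patient

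*SAP*

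**What the plan says.** SAP V.I.4 defines the PK Population as Safety Population patients "with at least one quantifiable pre-dose and one quantifiable post-dose PK plasma concentration". Protocol v2.0 gives the same two-part condition in section 10.2.2 and in the synopsis, so this is not a slip confined to the SAP.

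On dosing, the protocol synopsis states "All patients will receive 1 doses of tinostamustine on Days -1". On sampling, footnote 16 of the schedule of events (Table 1) states "Blood samples for PK are to be collected immediately pre-infusion of tinostamustine". The remaining samples follow the start of that infusion, at 30, 45 and 60 minutes and at 3, 6, 24 and 48 hours.

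On use of the set, protocol 10.2.9 states "PK analysis for tinostamustine and its metabolites will be performed using the PK set". SAP I.C drops Phase 2 after the halt ("neither the primary nor secondary objectives/endpoints will be explored") and lists the Phase 1 analyses that no longer apply; PK is not on that list. SAP VI.C plans counts and percentages for every analysis set, including the PK Population, by dose cohort and overall. SAP IX leaves PK analysis to a third-party vendor's separate report.

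**The concern.** With one dose per patient and one sample before it, nothing given in the study can produce a measurable pre-dose level. A value below quantification is what a properly drawn baseline should show, yet the rule treats it as grounds for exclusion. A patient would meet the condition mainly through contamination, a sample swap, a mistimed draw or assay interference. The rule therefore selects in the wrong direction.

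At stake is the Phase 1 secondary objective of describing tinostamustine PK. Followed as written, the protocol's PK analysis has essentially no patients. The SAP's table of analysis sets would then show a PK Population at or near zero, alongside a vendor report presumably based on patients who gave valid samples. The study report would have to explain that contradiction.

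**Working it through.** The plan states no figure for the size of the PK set, so there is nothing to reproduce. The check has three steps.

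**1. Could a pre-dose level be real?** The study gives no earlier dose. Protocol 9.4 speaks of sampling after each dose, but the schedule contains only one. Tinostamustine received before the study is not barred by name. However, exclusion criterion 10 rules out investigational anti-cancer agents in the 21 days before treatment, and the clarification memo of January 30, 2019 includes the words "Given the short half-life of tinostamustine". The documents give no half-life figure, so I assume a range:

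- Fraction left after 21 days (504 h) = 2^(−504 / half-life in hours).
- Half-life 6 h: 5 × 10⁻²⁶. Half-life 12 h: 2 × 10⁻¹³. Half-life 24 h: 5 × 10⁻⁷.

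Carry-over is negligible across this range.

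**2. Size of the set as written.** Inputs:

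- n = 9 to 12, the planned Phase 1 size (SAP III.C).
- p = probability that a pre-dose sample is quantifiable by anomaly. This is an assumption, because the documents give no rate.

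Membership also needs a quantifiable post-dose value, so the expected size is at most n × p and P(empty) is at least (1 − p)^n.

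| p | Expected size, n = 9 | P(empty), n = 9 | Expected size, n = 12 | P(empty), n = 12 |
|---|---|---|---|---|
| 0 | 0 | 1.00 | 0 | 1.00 |
| 0.01 | 0.09 | 0.91 | 0.12 | 0.89 |
| 0.02 | 0.18 | 0.83 | 0.24 | 0.78 |
| 0.05 | 0.45 | 0.63 | 0.60 | 0.54 |
| 0.10 | 0.90 | 0.39 | 1.20 | 0.28 |

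For example, 0.95⁹ = 0.63 and 0.95¹² = 0.54. If only 90% of patients had a quantifiable post-dose value, and this were independent of the pre-dose result, then at p = 0.05 and n = 9 P(empty) = (1 − 0.05 × 0.90)⁹ = 0.66. The table is therefore slightly generous to the rule.

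**3. Size of the set without the pre-dose condition.** Assume 90% to 100% of patients have at least one quantifiable post-dose value:

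- n = 9: 9 × 0.90 = 8.1, up to 9.
- n = 12: 12 × 0.90 = 10.8, up to 12.

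**The case against.** The strongest reply is that little depends on this set. In the SAP V.I table no analysis is marked against the Pharmacokinetic column, SAP IX places PK outside the SAP, PK is descriptive, and no escalation or efficacy rule uses the set. Phase 2 was dropped and the study was discontinued. Within the SAP, the visible effect is one row of counts. The vendor may apply its own definition, in which case the PK report would be unaffected. All of this stands, and it limits how serious the point is. It does not supply a working definition: protocol 10.2.9 ties the PK analysis to this set, and neither document says the vendor uses another.

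A second reply is that the probabilities rest on an assumed anomaly rate. That is true, and at 10% the set would more likely than not hold someone (P(empty) 39% or 28%). Even then it holds about one patient of 9 to 12 on average, and that patient would be there because of an anomalous sample. The conclusion does not depend on the rate chosen.

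A third reply is that the authors may have meant an available sample when they wrote quantifiable. That may be so. But the same word governs the post-dose condition, where its ordinary meaning fits, and neither document defines it otherwise or says how a below-limit pre-dose value counts towards membership.

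Finally, amending the protocol of a discontinued study may be disproportionate. That is fair, and the fix allows for it.

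**Conclusion.** The concern holds. As written, the PK set contains none of the 9 to 12 planned Phase 1 patients if their pre-dose samples are clean. It contains at most 0.45 to 0.60 on average if up to 5% of those samples are quantifiable by anomaly. Without the pre-dose condition it would hold about 8.1 to 9 of 9, or 10.8 to 12 of 12.

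These figures rest on the planned Phase 1 size, since the number actually dosed before the halt is not given, and on assumed rates of quantifiable pre-dose and post-dose samples. The central result, a set that is essentially empty on a literal reading, follows from the single dose and the sampling schedule alone. What happens in the vendor's PK report cannot be judged from these documents. This is a wrong rule that should be corrected, with limited consequences for the study as it now stands.

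**What to change.** - **SAP V.I.4:** remove the pre-dose condition, so that the PK Population is every Safety Population patient who has one or more quantifiable post-dose plasma concentrations. SAP I.B allows changes until database lock.
- **Pre-dose values:** treat any quantifiable pre-dose result as a data query, not as a condition for inclusion.
- **SAP IX:** add a line instructing the PK vendor to use the corrected definition, so that the vendor's report and the SAP VI.C table count the same patients.
- **Protocol 10.2.2 and synopsis:** make the same correction if the protocol is amended. If it is not, record the departure in the clinical study report, as protocol 10.3 provides.

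The cost is one sentence and one added line in the SAP, a short note to the vendor, and either a protocol correction with any approvals required under protocol 11.4 or an entry in the study report. Sampling and data collection do not change.
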